E.3. Recruitment and consent procedures: Patients recruitment will use IRB-approved recruitment materials, which advertise for regular or daily drinkers who want to reduce or stop their drinking. Distribution methods will include: informational brochures in UCHC and affiliated primary care and dental clinics; advertisements in local media (including text ads in newspapers, magazines; radio ads; web ads and web postings on community message boards); posting/distributing recruitment materials at local colleges with public posting areas or other means of communicating with students and staff, such as electronic bulletin boards; through broadcast email messages at institutions (such as UCHC, community agencies, local college campuses, etc.) that offer that type of service; by posting/distributing recruitment materials in community settings with public posting areas or other means of providing community access to materials (such as hospitals, town halls, public libraries, YMCA, health fairs/organizations). A partial waiver of consent and HIPAA Authorization will be obtained from the IRB to allow for preliminary phone screening for calls initiated by potential patients. Those individuals deemed eligible for in-person screening will sign a HIPAA Authorization and study consent form at their first visit. During the in-person screening visit each patient will receive an explanation of the study protocol, its risks, potential benefits, and alternative treatment by a study staff member. Following resolution of any questions, patients who appear to understand the nature of the study and consent will be asked to sign the study consent form. An entire copy of the informed consent form will be given to each patient. Because we will be recruiting patients from facilities throughout the Greater Hartford area, including outreach to the minority communities in the area, we anticipate that approximately 15% of patients enrolled in the study will be African-American and 10% will be Latino.

E.4. Potential risks: There are several classes of potential risk to patients enrolled in this study:

E.4.a. General Procedures: There is some risk that patients will be identified as participants in a study of treatment for heavy drinking or that the clinical assessments will adversely affect patients' well-being.

E.4.b. Counseling: Medical management brief counseling has been used safely with alcohol-dependent patients in the COMBINE Study. Psychological risks are minimal and not different from those of equivalent non-study treatments.

E.4.c. Medications: Dutasteride is not reinforcing and is therefore not a drug of abuse. There are few serious adverse effects associated with dutasteride use. Based on extensive clinical studies in men, dutasteride is well tolerated. In a series of three 2-year long treatment trials including 4,300 men aged 47-94 years (mean = 66 years), a 0.5 mg daily dose of dutasteride for treatment of enlarged prostate resulted in the following adverse effects compared with placebo: impotence (4.7% vs. 1.7%), decreased sex drive (3.0% vs. 1.4%), problems with ejaculation (1.4% vs. 0.5%), and enlargement of breast tissue (0.5% vs. 0.2%). 4% of dutasteride and 3% of placebo patients ended treatment due to a side effect concern. In other clinical studies, daily doses of 5 mg (i.e., 5 times the daily in the proposed study for alcohol problems) were administered to 60 men for 6 months with no adverse effects beyond those seen at the more commonly used daily dose of 0.5 mg (Avodart, Prescribing information 2012, GlaxoSmithKline). Dutasteride is not currently FDA approved for use in women

due to the potential risk of a specific birth defect (reduced size of male external genitalia). While it is theoretically possible to expose a pregnant women to dutasteride via semen, exposure of pregnant non-human primates intravenously to 16x the potential exposure to 5 ml of semen daily (assuming 100% absorption of dutasteride) was without adverse effect on the offspring (Avodart, Prescribing information 2006, GlaxoSmithKline). While no precautions are listed in the package insert regarding exposure of female partners to semen, we will advise participants to use medically acceptable contraceptives.

A large treatment trial involving over 6,000 men, "Reduction by Dutasteride of Prostate Cancer Events (REDUCE)" evaluated the daily use of dutasteride 0.5 mg versus placebo for 4 years to examine the effects of long-term treatment with dutasteride on the risk of prostate cancer in men over 50 years of age (Andriole et al. 2010). The trials demonstrated an overall reduction in prostate cancer diagnosis with dutasteride compared with placebo treatment (20% vs. 25% with placebo) but an increased incidence of high-grade (Gleason score 8-10) prostate cancer (1% for dutasteride vs. 0.5% for placebo) after 4 years. The increased incidence of high-grade cancer was not observed after 2 years exposure (0.5% for dutasteride vs. 0.5% for placebo). Long-term treatment with dutasteride may increase the risk for the development of high-grade prostate cancer. The 12-week short-term use of dutasteride in this study of alcohol use is not expected to alter participants' risk of prostate cancer.

E.4.d. Interaction of Medications and Alcohol: We have not observed any clinically significant additive CNS effects of dutasteride in combination with ethanol in our recently completed study of dutasteride paired with moderately intoxicating dose of alcohol in >70 male subjects (Covault et al. in preparation).

E.4.e. Blood and Urine Collection: These procedures are performed in large measure for baseline screening to safeguard patients. Additional bloods are drawn for research measures of alcohol and dutasteride effects. These procedures should add no risks other than those normally associated with these procedures, e.g., pain and bruising as a consequence of venipuncture.

E.4.f. Rating Scales and Questionnaires: These, including daily reports, are all non-invasive and add no special risk, although they do cover sensitive areas. The major disadvantages are the time taken to complete them, and possible breach of confidentiality. Our past experience indicates that these measures are acceptable to patients. Careful efforts to maintain confidentiality have been effective in our previous research and will be continued.

E.4.g. Genetic Testing. The principal risk of genetic testing is the potential for breach of confidentiality, with information concerning the patient's genetic risk for disease becoming known. Such information, if available to the patient, could cause distress and if available to health or life insurers could adversely affect the patient's access to insurance or its benefits. To guard against these risks, patients will not be provided with genetic test results and confidentiality will be closely protected as described below. Given the small likelihood of breach of confidentiality (NB: in over 10 years of genetic research by our ARC research group, we are not aware of a single instance of such a breach), the potential benefits accruing to the research (namely, a greater understanding of the genetic basis of alcohol use disorders and related psychiatric conditions and potentially of the genetic moderators of the response to treatment with dutasteride), and the complex nature of the disorders (limiting the impact that knowledge of any single genetic variant may have on disease risk), the potential benefit-to-risk ratio is favorable.

E.5. Procedures to minimize potential risks: Inclusion criteria and the use of trained research staff in initial screening will minimize acceptance of patients with insignificant alcohol use into the study. Careful pre-treatment evaluation by trained, experienced staff will minimize the risk of including individuals with contraindicated medical and/or psychiatric conditions. Experienced phlebotomists will minimize venipuncture risk. During treatment, patients' substance use and medical and psychiatric status will be closely monitored. Patients with breath alcohol levels over the legal driving limit or clinical evidence of intoxication will be examined by a study physician and monitored until no longer intoxicated, or referred for appropriate treatment, as clinically appropriate. Frequent contact will help identify patients with adverse treatment effects. Patients will be given a card identifying themselves as participants in a study involving dutasteride, and containing the emergency numbers of the PI and study physicians for 24-hour consultation. The medication blind will be broken if necessary for emergency assessment or treatment. For example, if the PI determines that an adverse event is serious, unexpected, possibly related to the study drug, and medical intervention is needed,

the PI will un-blind the data so that the patient can receive proper treatment. Adverse medication effects will be systematically evaluated and recorded. If serious, patients will be withdrawn from the study and given appropriate treatment and/or referral.

E.5.a. Confidentiality: To avoid breach of confidentiality, patients' names will appear only on a consent form, a telephone screening form and a "key" form kept by study staff in a locked cabinet. All forms that contain identifying information will be kept double locked (i.e., in a locked cabinet, in a locked room) to maintain their security. All study data forms will contain only the patient's unique study identification number. Prior to final study closure, any links between personal identifiers and each subjects unique study ID will be deleted to generate a de-identified dataset. Patient visits will be scheduled and no information about the patient will be provided to anyone (except in emergencies as defined above) in person or by telephone, except as required by law. The study will be conducted in an outpatient clinic in which treatment is provided to patients who have a variety of problems, not limited to substance abuse.

E.5.b. Alternative Treatments: The alternative procedures available are counseling by other clinicians, self-help groups such as Alcoholics Anonymous, or more intensive treatment for heavy drinking, including treatment with oral or long-acting injectable naltrexone, disulfiram, or acamprosate, which are all FDA-approved medications widely available for treatment of AD.

E.6. Anticipated benefits to patients and society: Benefits to patients include careful evaluation of their medical and psychiatric status and alcohol use and potential reduction in their alcohol consumption, which may improve their health and well-being. Benefits to society include a potential improvement in the effectiveness of treatment for problem drinking, which may reduce the personal and societal burdens associated with heavy drinking. In addition, clinicians and scientists may better understand the effects of dutasteride to reduce alcohol consumption. An improved understanding of the genetic and other moderators of dutasteride response will enhance the clinical utility of dutasteride for alcohol use problems and the process of medications development for alcohol treatment.

E.7. Comparison of risks and anticipated benefits to patients and society: The risks associated with the counseling are minimal. Although the medication presents some risk, it has been shown to be safe when administered for benign prostatic hypertrophy for long periods of time (years). The potential risks of these treatments are minor compared to the risk incurred by individuals who continue to drink heavily. The risk/benefit ratio thus appears favorable to the proposed treatments.

E.8. Data and Safety Monitoring Plan (DSMP): The DSMP is established to ensure the safety of research participants and the integrity of the study data. [name], M.D., the principal investigator of this study, or one of the other study physicians, will be charged with the duty of determining the severity rating of adverse events. The study staff (P.I., co-investigators, clinical research coordinator) are responsible for collecting and recording all clinical data. As these results are collected, all toxicities and adverse events will be identified, graded for severity and assigned causality, reported to the required entities, and compiled for periodic review. After assigning causality, the P.I. will decide the course of action for the study participant. The P.I. will evaluate every adverse event and determine whether it affects the risk/benefit ratio of the study and whether modifications to the protocol or informed consent form are required. The principal investigator (and, in his absence, physician co-investigators) will differentiate serious from non-serious adverse events. Serious adverse events that are related to the study interventions and unexpected will be reported to the UCHC IRB and the NIAAA project officer within 48 hours. An annual report summarizing all adverse events will be prepared and reported to the NIAAA project officer. The following information will be considered in the periodic safety report:

- Number of patients who have completed the study.
- Dropout rates and reasons for the dropouts.
- Summary of adverse events.
- Any other relevant information

Adverse events during the treatment will be reported to the UCHC IRB, as well as to the NIAAA on an annual basis, with serious adverse events that are related to the study interventions and unexpected being reported within 48 hours. Any patients thought to be at risk from drinking or psychiatric or medical disorders during

treatment or the follow-up period will be referred to services at UCHC or to other local health service providers. If it has been determined, for any reason, that the study should be suspended, we will discontinue enrollment of new patients, while continuing the treatment and monitoring of patients already enrolled in the study, unless to do so would create a risk that is not justified by any potential benefit to patients.

Women of Reproductive Age: As noted above women will not be included in this study as dutasteride is not FDA approved for use in women.

Data and Record Safety/Confidentiality: Records, filed in the IRB office, verify that all research project personnel have completed training in the protection of human research subjects in accordance with the guidelines of the U.S. Department of Health and Human Services (DHHS) and the Office for Human Research Protection (OHRP). The study staff (PI, Clinical research coordinator, etc.) will keep all study medical records containing personal identifiers in locked cabinets in a secure location. All electronic data and files (e.g., database, spreadsheet, etc.) containing identifiable patient information shall be password protected. Any computer hosting such files shall have a BIOS password to prevent access by un-authorized users. Furthermore, for systems not running Windows 2000/XP, a password-protected screen saver will be installed and configured to activate ten minutes after the computer has been idle. If patient data are to be exchanged with others, the data will be coded. If identification is necessary, then the data will be encrypted while en-route to the recipient with strong encryption levels (\geq 128 bits for symmetric encryption (DES) and \geq 1024 bits for asymmetric encryption (RSA)).

All research data and blood specimens will be stored without direct identifiable information and links to personal information will be destroyed at the end of the patients participation in the study to generate a de-identified dataset. Blood will not be used for the purpose of establishing cell lines. Any hard copy records associated with the study will be kept in locked offices in the Clinical Research Center or the Alcohol Research Center. The secured research records are labeled with code numbers only (names and other identifying information are kept separate from research records). Access to hard copy data is only given to staff members working on the study. Only staff members designated to handle or analyze study samples will have access to the samples and their storage. Coded blood samples are stored in clinic-specific refrigerators and freezers, which are located in secure rooms until transfer to the clinical or research laboratory

Blood will be collected for DNA analysis. The information derived from analysis of the patients' DNA will not be provided to the patient, since at the present time the existing preliminary genetic data for risk of alcohol dependence or in predicting response to dutasteride treatment do not provide a basis for genetic counseling. Should that situation change over the course of the treatment trial, procedures will be developed in conjunction with the UCHC IRB, to provide patients with relevant information on genotype and to counsel them in relation to that information. While the study is open, DNA samples will be coded with a number that provides an indirect link to the patient's identity (samples will be accessible only by the researchers and staff involved with this study). Upon completion of the study the sample will be kept in storage indefinitely. However, the sample will forever be separated from all personal identifiers. These de-identified samples may be shared with other researchers and used in other projects. The lab procedures for sample storage include a passcode-protected locked room, and/or secure storage freezers.

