breast tissue (0.5% vs. 0.2%). In other clinical studies, daily doses of 5 mg (i.e., 5 times the daily dose in the current proposed study) were administered to 60 subjects for 6 months with no adverse effects beyond those seen at the more commonly used daily dose of 0.5 mg. In studies of normal volunteers, doses of up to 40 mg daily of dutasteride for 7 days have been administered without significant adverse effects. Dutasteride is not currently FDA approved for use in women due to the potential risk of a specific birth defect (reduced size of male external genitalia).

C.3.b. Placebo drug will consist of lactose powder formulated by the Research Pharmacy Service in gelatin capsules indistinguishable from the capsules containing dutasteride.

C.3.c. Medication Randomization and Drug Accountability: The UCHC Research Pharmacy staff will be responsible for medication randomization and dispensing. The Research Pharmacy will enter randomization variables (age, AKR1C3 genotype, frequency of heavy drinking days for the 90-day period prior to screening, number of DSM-IV AD criteria, use of medication for treatment of co-morbid psychiatric condition, and drinks per drinking day from baseline 90-day TLFB) into an urn randomization program and provide to study staff a supply of study drug, as assigned. Although we will monitor capsule counts at each treatment visit, our primary measure of medication adherence will be daily IVR reports (section D.6.b.2). A daily diary method has been shown to yield results that are comparable to those obtained with electronic monitoring ($r = .91$) (Feinn et al. 2003).

C.4. Study Visits:

C.4.a. Visit 1 (Screening Visit): Prior to informed consent, subjects will have a breath alcohol (BrAC) measurement to validate sobriety. Following completion of informed consent, a brief medical and psychiatric history will be obtained by a study research assistant or nurse. Blood and urine samples will be taken for routine clinical laboratory evaluations, drug screening, DNA extraction and measurement of serum outcome measures GGT, %dCDT, the neuroactive steroid metabolite 3α -diolG and testosterone (to monitor for any unexpected negative effects of dutasteride on testosterone in heavy drinkers). Relevant portions of the Structured Clinical Interview for DSM-IV (SCID-I) will be administered by a research assistant to screen out subjects with major mental illness or dependence on other than alcohol or tobacco.

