At the end of treatment week 12 (visit 8), subjects will complete a packet of questionnaires and be interviewed by research staff concerning their alcohol consumption and alcohol-related symptomatology (using the Alcohol section of the SCID-I, modified to ask about the past 30 days). Subjects will be compensated \$50 for this end-of-treatment visit. Subjects requesting additional treatment for alcohol problems will be referred to local treatment centers. For subjects who withdraw early and do not wish to continue with study visits/procedures, all end-of-treatment procedures will be administered at the time of withdrawal. Such subjects will also be invited to participate in-person or by telephone to provide Timeline Followback data at 2, 4, and 6-months post-treatment.

C.4.d. Visit 9, 10, and 11 (Post-treatment Assessment Visits): To evaluate the durability of treatment effects, patients will return to the clinic for post-treatment assessments 2,4, and 6-months after completion (or for early terminators, scheduled completion) of treatment. We will attempt to reach all subjects directly or via their locator. At this visit, the subject will complete the self-report packet of questionnaires and will be interviewed by the research staff. Blood samples for measurement of serum GGT, %dCDT and 3 α -diolG will be obtained. Subjects will be paid \$50 for the two and four month post treatment visit and \$75 for the six month post-treatment assessment visits. Subjects will be eligible to request drug assignment information after their 6-month post-treatment assessment.

C.5. Medical Management: The physician will meet with the subject at the beginning of treatment and will consult at least weekly with the study staff to monitor potential study related side effects and adverse event occurrence. The physician will evaluate the subject should severe or persistent adverse effects occur. At each treatment visit (2-7) subjects will receive brief counseling as part of medical management, which is described in detail below.

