d. *Daily Events:* Participants will be asked whether they experienced a list of nine possible daily events (3 stressful, 3 pleasant, and 3 situations where someone might drink). These measures will be used to assess the influence of positive and negative events on drinking.

e. *Daily medication usage:* Using IVR, subjects will report daily medication use. Additionally, at each bi-weekly study visit, subjects will be asked by the study staff to indicate the number of study drug capsules taken each day. This method has been shown to be highly correlated with electronic monitoring of medication adherence (Feinn et al. 2003).

C.6.b.3. Areas assessed biweekly during the active treatment period and follow up visits:

a. *Alcohol use patterns:* The TLFB (Sobell and Sobell 1992) will be used to estimate drinking at intake, at each biweekly study visit during the active treatment period and at each of the two follow-up evaluations. This interview procedure will provide quantity/frequency of alcohol consumption data for each day during the period prior to the interview. We will also be collecting daily measures of alcohol consumption using IVR during the active treatment period because despite evidence of the reliability and validity of the TLFB when used by trained interviewers, the TLFB is less useful for detecting patterns of alcohol consumption that vary on a day-to-day basis (Carney et al. 1998; Searles et al. 2000). Daily IVR reports will also enable us to examine co-variation in daily mood and daily events with alcohol use in order to address whether dutasteride moderates associations between daily mood or daily events and drinking as our group has found using IVR methods for treatment with naltrexone (Kranzler et al. 2004; Armeli et al. 2006).

b. *Alcohol Craving:* The Penn Alcohol Craving Scale (PACS) is a 5-item self-report measure that includes questions regarding the frequency, intensity, and duration of craving over the past week as well (Flannery et al., 1999). The PACS has been shown to predict subsequent drinking during alcohol treatment trials (Flannery et al., 1999, 2003).

c. *Medication adverse effects:* Subjects will provide reports of side effects at each bi-weekly phone visit and study visit during the active treatment phase and 2-month follow-up visit using a list of adverse medication

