C.8.a.1. Safety: Safety will be analyzed using categorical outcomes, defined by the type and severity of adverse effects. Summary measures of adverse events (AEs) will be developed by organ system from the adverse event checklist and will be compared for patients receiving dutasteride or placebo using χ^2 analysis. Comparisons will be conducted on 1) the number of patients in each of the two groups who report AEs, 2) the number of patients in each of the two groups who report moderate-to-severe AEs, and 3) the number of patients in each group who discontinue treatment due to AEs. Individual AEs that occur in $\geq 5\%$ of patients in either medication condition will be examined using χ^2 analysis.

C.8.a.2. Efficacy: An important initial consideration will be to identify baseline differences between groups that may have occurred despite the use of urn randomization. The distribution of outcome data will also be examined prior to analysis, to determine the need for transformation and whether parametric analytic methods can be utilized. Successful outcome will be defined in terms of three primary dependent measures: SDs/week, HDDs/week, % of subjects with no HDDs, and % of subjects with non-hazardous drinking (no HDDs and SDs/week <15). Patients will be followed irrespective of whether they continue to receive treatment, so that analysis of both primary drinking measures and secondary outcomes will include all data available for the 12-week treatment period. Data for analyses of drinking outcomes during the 12-week treatment period will come from the daily IVR reports (missing IVR report days which will be coded as the larger of either 5 standard drinks (i.e. a HDD) or the IVR average daily use for the week reporting interval). Analysis of drinking for the 6-month follow-up period will be based on TLFB data collected at each follow-up visit. Secondary outcomes will include mean daily alcohol consumption, %dCDT levels (change relative to baseline), and severity of alcohol-related problems (as measured on the SIP and number of DSM-IV AD criteria).

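### E.5 takes men with serious adverse medication effects out of the study, which conflicts with the promise in C.8.a.2 to follow patients whether or not they stay on treatment; the effect is small and a wording change fixes it

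*Combined protocol and SAP*

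**What the plan says.** Section E.5 (procedures to minimize risks), having said that adverse medication effects will be evaluated and recorded, instructs: "If serious, patients will be withdrawn from the study and given appropriate treatment and/or referral".

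Section C.8.a.2 (efficacy) takes the opposite line: "Patients will be followed irrespective of whether they continue to receive treatment". The stated purpose is that analyses use all data available for the 12 weeks. The source is named: "Data for analyses of drinking outcomes during the 12-week treatment period will come from the daily IVR reports". A missing IVR day is coded as 5 standard drinks, which is a heavy drinking day (HDD), or as the man's IVR average for that week if larger. Three analysis conditions follow: all information provided, completers only, and missing days of non-completers coded as HDDs.

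The only operational rule for early exit is in C.4.c. It opens "For subjects who withdraw early and do not wish to continue with study visits/procedures", and provides end-of-treatment procedures at withdrawal and an invitation to give TLFB at 2, 4 and 6 months after treatment. C.4.d dates those visits from scheduled completion for early terminators and adds: "We will attempt to reach all subjects directly or via their locator". In E.8, the decision after an adverse event rests with the principal investigator: "After assigning causality, the P.I. will decide the course of action for the study participant".

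**The concern.** Staff managing a serious adverse effect would turn to the safety section, not to the analysis section. Applied as written, E.5 ends a man's participation and with it his daily IVR reports, although C.8.a.2 relies on those reports for everyone, on or off medication.

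The lost days are not neutral in this plan, because missing IVR days are scored as heavy drinking. The plan does not say whether that coding runs on after a man has left the study. If it does, a man withdrawn for safety is counted as a heavy drinker on every remaining day. He then fails two of the listed primary measures: having no HDDs, and non-hazardous drinking (no HDDs and fewer than 15 drinks per week).

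**Working it through.** **1. The sections side by side.**
- E.5: a serious adverse medication effect leads to withdrawal from the study.
- C.8.a.2: follow-up continues off treatment, with no exception for stops made by the investigators.
- C.4.c: covers men who leave early and do not want further visits. Men withdrawn by the investigators are not named. Even for those it covers, it provides no IVR or biweekly TLFB between exit and week 12.
- C.4.d: tries to reach everyone, but for the post-treatment visits.
- E.8: leaves the decision to the investigator and does not mention data collection.

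The general promise therefore exists, but E.5 contradicts it and no operational section carries it through for these men.

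**2. The plan's own figure (C.8.b).** With 80 completers per arm, d = 0.45 and alpha 0.05 (two-sided assumed), a two-sample t-test has power 0.808, or 0.812 by the normal approximation. The stated 80% reproduces. The plan randomizes 176 to obtain 160 completers, so 176 − 160 = 16 non-completers (16/176 = 9.1%) are already budgeted. A man withdrawn under E.5 would normally be one of those 16.

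**3. Responder-type measures, per man.** Assuming equal arms, 176/2 = 88 men per arm. If lost days are coded as HDDs, one man is 1/88 = 1.1 percentage points on each of the two measures. This is a ceiling on the change, since he alters the percentage only if he would otherwise have counted as a success.

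**4. HDDs per week, per net extra man in one arm.** Shift in the arm's 12-week mean = (1/88) × (7 − true HDD/week) × (weeks lost/12). The exit week and true level are assumptions. The SD of 1.9 and the upper level of 5.1 are the pilot's study-entry figures (C.1.c).

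| Exit after | True HDD/week | Shift | Shift/1.9 |
|---|---|---|---|
| week 2 | 0 | 0.066 | 0.035 |
| week 2 | 3 | 0.038 | 0.020 |
| week 2 | 5.1 | 0.018 | 0.009 |
| week 6 | 0 | 0.040 | 0.021 |
| week 6 | 3 | 0.023 | 0.012 |
| week 6 | 5.1 | 0.011 | 0.006 |

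For example, (1/88) × (7 − 3) × (10/12) = 0.038. The contrast is zero if the arms lose equal numbers with similar profiles, and it changes sign if the extra man is on placebo. It concerns the 12-week mean, not the group-by-week interaction that the plan tests.

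**5. Data lost.** Exit after week 2 loses 10 of 88 × 12 = 1,056 person-weeks in an arm, or 0.9%.

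**6. Could TLFB recover the gap?** C.6.b.3 says: "This interview procedure will provide quantity/frequency of alcohol consumption data for each day during the period prior to the interview". No look-back length is set for an early leaver's 2-month visit. Taking 2 months as 61 days, the look-back needed is (12 − exit week) × 7 + 61: 131 days after a week-2 exit, 103 after week 6 and 75 after week 10. The one TLFB length stated is the 90-day baseline window (C.3.c: "drinks per drinking day from baseline 90-day TLFB"). Recovery is neither promised nor excluded.

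**The case against.** The strongest reply is that E.5 means stopping the drug. C.8.a.1 counts patients who stop treatment because of adverse events, and C.6.b.4 schedules the medication questionnaire at treatment discontinuation. C.4.c ends visits only for men who do not want to go on, which makes continuing the default. C.8.a.2 already gives a general follow-up promise. Against all this stands one sentence in the human-subjects section, written for patient care. This stands as a reading of intent, and it is a reason to correct E.5, because the sentence that staff would act on says something else.

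It is also fair that the plan already handles missing data: C.8.a.2 has a coding rule and three analysis conditions, and the mixed model keeps a man's earlier weeks. That limits the damage but does not replace reports that could have been collected.

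A reader might infer three stronger points that the documents do not support:
- **Lost power.** Subtracting such men from the 80 completers per arm would count the budgeted dropout twice.
- **Bias against dutasteride.** E.4.c reports that 4% on dutasteride and 3% on placebo ended treatment over a side-effect concern. Those figures cover any such concern, over two years, at 0.5 mg daily. They give no rate of serious effects and no arm difference for this trial.
- **Abandoned patients.** E.5 provides treatment or referral, and C.4.d seeks post-treatment contact with everyone.

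**Conclusion.** The conflict is real, and minor. E.5 as written would end treatment-period IVR for men with serious adverse medication effects, contrary to C.8.a.2, and no other section states that it continues for them.

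The size is up to about 1.1 percentage points per man on each responder-type measure in an 88-man arm. For one net extra man it is 0.011 to 0.066 HDD/week (0.006 to 0.035 of the pilot SD). Both rest on the assumption that lost days are coded as HDDs; the second also rests on the assumed exit weeks and drinking levels.

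The documents give no rate of serious effects. E.4.c expects few, and none of the 3 dropouts among the pilot's 39 randomized men was due to side effects. The stated sample size and power stand.

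**What to change.** In E.5, make the withdrawal one from study medication. State that daily IVR, biweekly TLFB and safety follow-up continue to week 12 and through post-treatment follow-up unless the man withdraws consent. If he stops calling, the next TLFB should look back to his last IVR report. Flag reports made after unblinding.

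The cost is one or two sentences and continued contact with a few men. The consent form was not available for this review, so the sponsor should check that its wording agrees. The downside is that E.5 allows the blind to be broken for some of these men, so their later self-reports may not be blinded. The change has to be made prospectively, because daily reports that were never collected cannot be fully recovered.
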